#### **5.4.2.6 Pregnancy**

If a female subject becomes pregnant while receiving Xofluza or within 14 days after the last dose of Xofluza, or if the female partner of a male study subject becomes pregnant while the study subject is receiving Xofluza or within 14 days, a report should be completed and expeditiously submitted to Genentech, Inc. Pregnancies will be followed-up until the outcome of the pregnancy is known, whenever possible, based upon due diligence taken to obtain the follow-up information. Abortion, whether accidental,

therapeutic, or spontaneous, should always be classified as serious, and expeditiously reported as an SAE. Similarly, any congenital anomaly/birth defect in a child born to a female subject exposed to Xofluza should be reported as an SAE.

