#### **4.1.1 Inclusion Criteria**

Patients must meet the following criteria for study entry:

- Adult patients: Signed informed consent by any patient capable of giving consent, or, where the patient is not capable of giving consent, by his or her legal/authorized representative.
- Adolescent patients not able to legally consent: written informed consent for study participation is obtained from patient's parents or legal guardian, with assent as appropriate by the patient, depending on the patient's level of understanding and capability to provide assent
- Age  $\geq$  5 years at the time of signing the Informed Consent Form/Accent Form
- Ability to comply with the study protocol, in the investigator's judgment.
- Presence of (a) fever ( $\geq$ 38.0 °C per tympanic or rectal thermometer;  $\geq$ 37.5 °C per axillary, oral or forehead/temporal thermometer) or (b) any influenza symptoms (cough, sore throat, nasal congestion, headache, feverishness or chills, muscle or joint pain, fatigue).
- The time interval between the onset of fever or influenza symptoms and the pre-dose examinations is 48 hours or less.
- For women of childbearing potential: Agreement to remain abstinent (refrain from heterosexual intercourse):

Women must remain abstinent or use contraceptive methods with a failure rate of < 1% per year during the treatment period and for 28 days after the last dose of study treatment. Hormonal contraceptive methods must be supplemented by a barrier method.

A woman is considered to be of childbearing potential if she is postmenarcheal, has not reached a postmenopausal state ( $\geq 12$  continuous months of amenorrhea with no identified cause other than menopause), and has not undergone surgical sterilization (removal of ovaries and/or uterus).

Examples of contraceptive methods with a failure rate of  $< 1\%$  per year include bilateral tubal ligation, male sterilization, hormonal contraceptives that inhibit ovulation, hormone-releasing intrauterine devices, and copper intrauterine devices.

The reliability of sexual abstinence should be evaluated in relation to the duration of the clinical trial and the preferred and usual lifestyle of the patient. Periodic abstinence (e.g., calendar, ovulation, symptothermal, or postovulation methods) and withdrawal are not acceptable methods of contraception.

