#### **4.1.2 Exclusion Criteria**

Patients who meet any of the following criteria will be excluded from study entry:

- Patients who have received more than 48 hours of antiviral treatment for the current influenza infection prior to screening
- Patients who have received Xofluza for the current influenza infection
- Known contraindication to neuraminidase inhibitors
- Patients weighing  $< 20$  kg
- Patients unable to swallow tablets
- Patients with known severe renal impairment (estimated glomerular filtration rate  $< 30$  mL/min/1.73 m $^2$ ) or receiving continuous renal replacement therapy, hemodialysis, peritoneal dialysis
- Patients with any of the following laboratory abnormalities detected within 24 hours prior to or during screening (according to local laboratory reference ranges:
  - ALT or AST level  $> 5$  times the upper limit of normal (ULN)  
OR
  - ALT or AST  $> 3$  times the ULN and total bilirubin level  $> 2$  times the ULN
- Pregnant or breastfeeding, or positive pregnancy test in a predose examination, or intending to become pregnant during the study or within 28 days after the last dose of study treatment
- Exposure to an investigational drug within 5 half-lives or 30 days (whichever is longer) of randomization
- Any serious medical condition or abnormality in clinical laboratory tests that, in the investigator's judgment, precludes the patient's safe participation in and completion of the study
- Known hypersensitivity to Xofluza (baloxavir marboxil) or the drug product excipients

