### **5.3.1        Adverse Event Reporting Period**

The study period during which AEs and SAEs as described in Section 5.4.2.10 where the patient has been exposed to Genentech product must be reported - reporting period begins after informed consent is obtained and initiation of study treatment and ends 14 days following the last administration of study treatment or study discontinuation/termination, whichever is earlier. After this period, investigators should only report SAEs that are attributed to prior study treatment (Modify statement depending up on AESI Section 5.4.2.7.

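### Women are asked to avoid pregnancy for 28 days after the dose, but the explicit trigger for a pregnancy report stops at 14 days

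*Combined protocol and SAP*

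**What the plan says.** **Avoidance period.** The contraception criterion in section 4.1.1 states: "Women must remain abstinent or use contraceptive methods with a failure rate of < 1% per year", and the period is "during the treatment period and for 28 days after the last dose of study treatment". The exclusion criteria in section 4.1.2 use the same length and rule out women "intending to become pregnant during the study or within 28 days after the last dose of study treatment".

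**Reporting trigger.** Section 5.4.2.6 asks for an expeditious report to the drug's manufacturer under this condition: "If a female subject becomes pregnant while receiving Xofluza or within 14 days after the last dose of Xofluza". The same 14 days apply to the female partner of a male subject. The section continues: "Pregnancies will be followed-up until the outcome of the pregnancy is known, whenever possible". It adds that an abortion, whether accidental, "therapeutic, or spontaneous, should always be classified as serious, and expeditiously reported as an SAE", and that "any congenital anomaly/birth defect in a child born to a female subject exposed to Xofluza should be reported as an SAE". None of these later sentences states a day limit.

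**General safety window.** Under section 5.3.1 the period for adverse events "ends 14 days following the last administration of study treatment or study discontinuation/termination, whichever is earlier". After that, only serious events attributed to the study drug are to be reported.

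**Dosing and contact.** Treatment is one oral dose (section 3.1). The last scheduled contact is the phone call 14 days after the screening visit (section 3.2).

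**The concern.** Treatment is a single dose, so the 28-day and 14-day clocks start together and can be compared directly. The protocol regards exposure as relevant enough to conception that women should avoid pregnancy through day 28. Its explicit request for a report covers only the first half of that period. No rationale for the shorter window is given.

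If a woman conceives on, say, day 20 and the pregnancy runs without complication, site staff who apply 5.4.2.6 as written have no clear instruction to notify it or to obtain its outcome. What is at stake is the completeness of information on drug-exposed pregnancies. No efficacy result depends on it.

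**Working it through.** **Step 1: compare the windows.** Both run from the same dose.

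| Rule | Section | Days after dose |
|---|---|---|
| Abstinence or contraception | 4.1.1 | 28 |
| No intention to become pregnant | 4.1.2 | 28 |
| Pregnancy report, female subject | 5.4.2.6 | 14 |
| General adverse event period | 5.3.1 | 14, or earlier on discontinuation or termination |

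Uncovered interval: 28 − 14 = 14 days (days 15 to 28), and 14/28 = 50% of the avoidance period.

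**Step 2: does another section cover an uncomplicated conception on days 15 to 28?**

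- 5.3.1: no. It ends at 14 days and then keeps only attributed serious events.
- 5.4.2.10: no. It covers attributed serious events, and cancer or a congenital anomaly in later-conceived offspring, but not the pregnancy itself.
- 5.4.2.8: no. Its list of special situations includes use during breastfeeding but not pregnancy.
- 5.4.2.11: unclear. It makes the sponsor responsible for collecting pregnancy reports where the patient was exposed, and sets a deadline of 30 calendar days from awareness. It gives no conception window.

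**Step 3: how many pregnancies could fall in the interval?** The documents give no share of women of childbearing potential, so every treated patient is counted as one. This overstates the number, since males and children from age 5 can be treated. The annual rate is the 1% contraceptive-failure limit in 4.1.1. The numbers treated are the 54 to 180 printed in the table in 6.1.

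Expected pregnancies on days 15 to 28 = N × 0.01 × 14/365.

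- N = 54: 54 × 0.01 × 14/365 = 0.021
- N = 180: 180 × 0.01 × 14/365 = 0.069

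The text of 6.1 also mentions about 430 treated. That would give 430 × 0.01 × 14/365 = 0.16, but it disagrees with the table.

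**Step 4: sensitivity to non-adherence.** The count is proportional to the annual rate, and the documents give no rate for women who do not follow the rule. With 180 treated, the interval holds 180 × 14/365 = 6.9 person-years. The annual rate would have to reach 1/6.9, about 14.5%, before one pregnancy was expected, even with every patient counted as a woman of childbearing potential.

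**Step 5: effect of the change.** With 28 days in 5.4.2.6, the uncovered interval is 28 − 28 = 0 days.

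**The case against.** **The two windows do different jobs.** One sets contraceptive caution. The other sets a notification trigger and matches the 14-day adverse event period in 5.3.1. Both can be followed at once, and nothing in the documents says they must be equal. This stands: the plan does not contradict itself, and the point is one of alignment.

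**Section 5.4.2.11 may already cover the case.** Its stated condition is exposure to the product, with no day limit, so a reasonable reader could submit a day-20 conception under it. This stands in part. Another reader could take the term to mean the pregnancy reports defined in 5.4.2.6, with their 14 days. If the wider reading is right, it sits awkwardly beside 5.4.2.6, and staff still need one number.

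**A reader might infer that the record for days 15 to 28 would hold abortions and anomalies without the normal pregnancies as denominator.** The documents do not support that. It requires treating the abortion sentence in 5.4.2.6 as unlimited while confining the follow-up sentence to 14 days, although neither carries a day limit. Read consistently, either both are bounded by the opening condition or neither is. With well under one pregnancy expected, a missing denominator would also have no practical meaning.

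**A reader might also count the lack of a pregnancy question in the 14-day survey (Appendix 1) as part of the gap.** It is not: a question asked on day 14 cannot detect a conception on days 15 to 28.

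**Conclusion.** The point holds as a minor safety-reporting alignment. An uncomplicated pregnancy in a female subject conceived on days 15 to 28 lies within the protocol's own avoidance period and outside the explicit trigger in 5.4.2.6, and no other section clearly brings it in. The interval is 14 of 28 days. The expected count is at most about 0.02 to 0.07 for the whole study, given adherence to the 1% per year limit, 54 to 180 treated, and every treated patient counted as a woman of childbearing potential. Non-adherence would raise it by an amount the documents do not allow one to state.

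The mismatch concerns female subjects only. The criteria set no contraception rule for male subjects, so the 14-day partner window has nothing to disagree with. Nor does the gap reach every event after day 14: serious events attributed to the drug, and congenital anomalies in offspring of exposed women, remain reportable. Sample size and the primary analysis are untouched.

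**What to change.** 1. In 5.4.2.6, change 14 to 28 days for female subjects. Leave the partner window as written.
2. In 5.3.1, add a sentence such as: *Pregnancies in female subjects conceived up to 28 days after the dose are reportable under 5.4.2.6 whenever they are recognised.*
3. In the counselling already given at dosing (3.1) and in the existing day-14 call (3.2), tell women of childbearing potential to report any pregnancy conceived up to day 28, even if it is recognised later.

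The cost is one number, one sentence and one instruction within contacts that already take place. No visit or test is added, and the transmission deadline in 5.4.2.11 need not change because it runs from awareness. The downside is that detection after day 14 relies on self-report, since no later contact is scheduled.

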#### **5.4.2.7 Adverse Events of Special Interest**

Adverse events of special interest (AESIs) are a subset of events to monitor (EtMs) of scientific and medical concern specific to the product, for which ongoing monitoring and rapid communication by the Investigator to the Sponsor is required. Such an event might require further investigation in order to characterize and understand it. Depending on the nature of the event, rapid communication by the trial Sponsor to other parties (e.g., Regulatory Authorities) may also be warranted.

AESIs for this study include the following:

- Cases of potential drug-induced liver injury that include an elevated ALT or AST in combination with either an elevated bilirubin or clinical jaundice, as defined by Hy's law:
  - Treatment-emergent ALT or AST  $>3 \times$  ULN in combination with total bilirubin  $>2 \times$  ULN.
  - Treatment-emergent ALT or AST  $>3 \times$  ULN in combination with clinical jaundice.
- Data related to a suspected transmission of an infectious agent by the study drug (STIAMP), as defined below:

Any organism, virus, or infectious particle (e.g., prion protein transmitting transmissible spongiform encephalopathy), pathogenic or non-pathogenic, is considered an infectious agent. A transmission of an infectious agent may be suspected from clinical symptoms or laboratory findings that indicate an infection in a patient exposed to a medicinal product. This term applies only when a contamination of the study drug is suspected.

There are no products specific AESIs for Xofluza.

#### **5.4.2.8 Other Special Situations Reports**

The following other Special Situations Reports should be collected even in the absence of an Adverse Event and transmitted to Genentech:

- Data related to the Product usage during breastfeeding
- Data related to overdose, abuse, misuse or medication error (including potentially exposed or intercepted medication errors)
- In addition, reasonable attempts should be made to obtain and submit the age or age group of the patient, in order to be able to identify potential safety signals specific to a particular population

#### **5.4.2.9 Product Complaints**

A product complaint is defined as any written or oral information received from a complainant that alleges deficiencies related to identity, quality, safety, strength, purity, reliability, durability, effectiveness, or performance of a product after it has been released and distributed to the commercial market or clinical trial.

#### **5.4.2.10 Post-Study Adverse Events**

The investigator should expeditiously report any SAE occurring after a subject has completed or discontinued study participation if attributed to prior Xofluza exposure. If the investigator should become aware of the development of cancer or a congenital anomaly in a subsequently conceived offspring of a female subject [add if applicable: (including pregnancy occurring in the partner of a male study subject)] who participated in the study, this should be reported as an SAE adequately to Genentech Patient Safety during the follow-up period.

#### **5.4.2.11 Exchange of Single Case Reports with Genentech**

TriCore Laboratories will be responsible for collecting all protocol-defined Adverse Events (AEs)/Serious Adverse Events (SAEs), pregnancy reports (including pregnancy occurring in the partner of a male study subject), other Special Situation reports, AESIs and Product Complaints with an AE where the patient has been exposed to the Product. The Roche reporting Tool (AE reporting online “AERO”) should be sent to the Genentech contact specified below. Transmission of these reports (initial and follow-up) will be either electronically via email or by fax and within the timelines specified below:

**[contact]**

**Email: [usds\\[contact]](mailto:[contact])**

Batch ID/lot ID for biologics associated with AE/SSR/PC/AESI must be included when submitting the case reports to Genentech.

All Product Complaints without an AE should call via:

PC [contact] (M-F: 5 a.m. to 5 p.m. PST)

Transmission of these reports (initial and follow-up) will be either electronically or by fax and within the timelines specified below:

Type of Report	Timelines
Serious Adverse Events (related and not related to the Product)	
Special Situation Reports (With or without AE and pregnancy)	30 calendar days from awareness date
Product Complaints (With or without AE)	
AESI	

**[contact] / Email: [usds\\[contact]](mailto:[contact])**

#### **5.4.2.12 Case Transmission Verification of Single Case Reports**

*If Single Case Reports are exchanged via AERO, use the following:*

- Roche shall extract and review the AERO report listing on a quarterly basis. If any Single Case Report(s) is not correctly transmitted, Roche will request TriCore to immediately re-send the missing Single Case Report(s) and follow-up until resolution.

Monthly or quarterly line listings, Non-serious line listings, and cumulative/final CTV should be sent to: [[contact]](mailto:[contact])

#### **5.5 REPORTING REQUIREMENTS FOR ADVERSE EVENTS ORIGINATING FROM PATIENT-REPORTED OUTCOMES**

Although sites are not expected to review the PRO data, if physician/study personnel become aware of a potential adverse event during site review of the PRO questionnaire data, he/she will determine whether the criteria for an adverse event have been met and, if so, these must be reported using the Adverse Event and Special Situation Reporting Form or MedWatch form.

#### **5.6 MEDWATCH 3500A REPORTING GUIDELINES**

In addition to completing appropriate patient demographics (Section A) and suspect medication information (Sections C & D), the report should include the following information within the Event Description (Section B.5) of the MedWatch 3500A form:

- Protocol number and title description
- Description of event, severity, treatment, and outcome if known
- Supportive laboratory results and diagnostics (Section B.6)
- Investigator's assessment of the relationship of the adverse event to each investigational product and suspect medication

##### **5.6.1 Follow-Up Information**

Additional information may be added to a previously submitted report by any of the following methods:

- Adding to the original MedWatch 3500A report and submitting it as follow-up
- Adding supplemental summary information and submitting it as follow-up with the original MedWatch 3500A form
- Summarizing new information and faxing it with a cover letter including patient identifiers (i.e., D.O.B., initials, patient number), protocol description and number, if assigned, brief adverse event description, and notation that additional or follow-up information is being submitted (the patient identifiers are important so that the new information is added to the correct initial report)

MedWatch 3500A (Mandatory Reporting) form is available at  
<https://www.fda.gov/media/69876/download>

## **5.7 REPORTING TO REGULATORY AUTHORITIES, ETHICS COMMITTEES AND INVESTIGATORS**

Genentech, as the Marketing Authorization Holder, will be responsible for the reporting of individual case safety reports from the study to the regulatory authority in compliance with applicable regulations.

TriCore as the Sponsor of the study will be responsible for the expedited reporting of safety reports originating from the study to the European Medicine Agency (EMA) through Eudravigilance Clinical Trial Module (EVCTM), where applicable.

TriCore will be responsible for the expedited reporting of safety reports originating from the study to the Independent Ethics Committees/Institutional Review Boards (IEC/IRB) of the Concerned Member States, where applicable.

TriCore as the Sponsor of the study will be responsible for the preparation of six-monthly Suspected Unexpected Serious Adverse Reaction (SUSAR) reports and their submission to Investigators, Regulatory Authorities, and the Institutional Review Board/Independent Ethics Committee (IRB/IEC), where applicable.

TriCore will be responsible for the distribution of safety information to its own investigators, where relevant, in accordance with local regulations.

And TriCore will be responsible for the distribution of safety information to site IRB:

*WCG IRB*

## **5.8 AGGREGATE REPORTS**

### **Development Safety Update Report**

The Parties agree that aggregate reporting obligations for the study (including Development Safety Update Report [DSURs] and/or Investigational New Drug [IND] Annual Reports) in accordance with the applicable laws and regulations in the concerned countries will reside with TriCore, as the Sponsor of the study.

Upon request, TriCore, agrees to share a copy of their own DSUR with Genentech as soon as reasonably possible after completion.

Genentech will forward to TriCore an executive summary of the Genentech DSUR upon request. Furthermore, Genentech agrees that TriCore may cross-reference the executive summary of the Genentech DSUR, as applicable.

## **Other Reports**

TriCore will forward a copy of the final study report to Genentech upon completion of the study.

*Note: Investigators should also report events to their IRB as required.*

## **5.9 STUDY CLOSE-OUT**

Any study report submitted to the FDA by the Sponsor-Investigator should be copied to Genentech. This includes all IND annual reports and the Clinical Study Report (final study report). Additionally, any literature articles that are a result of the study should be sent to Genentech. Copies of such reports should be mailed to the assigned Clinical Operations contact for the study:

[[contact]](mailto:[contact])

And to Genentech Patient Safety CTV oversight mailbox at: [[contact]](mailto:[contact])

## **5.10 QUERIES**

Queries related to the study will be answered by TriCore. However, responses to all safety queries from Regulatory Authorities, Ethics Committees, and Institutional Review Board, or for publications will be discussed and coordinated between the Parties. The Parties agree that Genentech shall have the final say and control over safety queries relating to the Product. TriCore agrees that it shall not answer such queries from regulatory authorities and other sources relating to the Product independently but shall redirect such queries to Genentech.

Both Parties will use all reasonable effort to ensure that deadlines for responses to urgent requests from Regulatory Authorities and/or IRB/IEC for information or review of data are met. The Parties will clearly indicate on the request the reason for urgency and the date by which a response is required.

